### **17.2.5. Reporting of Pregnancy and Lactation**

Although pregnancy and lactation are not considered adverse events, it is the responsibility of investigators or their designees to report any pregnancy or lactation in a patient (spontaneously reported to them) that occurs during the study. Sites may use the pregnancy form in Rave EDC to report pregnancies.

Pregnancies and lactations that occur after the consent form is signed but before treatment allocation/randomization must be reported by the investigator if they cause the subject to be excluded from the study, or are the result of a protocol-specified intervention, including but not limited to washout or discontinuation of usual therapy, diet, placebo treatment or a procedure.

Pregnancies and lactations that occur from the time of treatment allocation/randomization through 120 days following cessation of pembrolizumab, or 30 days following cessation of treatment if the subject initiates new anticancer therapy, whichever is earlier, must be reported by the investigator. All pregnancies must be followed to the completion/termination of the pregnancy. Pregnancy outcomes of spontaneous abortion, missed abortion, benign hydatidiform mole, blighted ovum, fetal death, intrauterine death, miscarriage and stillbirth must be reported as serious events (Important Medical Events). If the pregnancy continues to term, the outcome (health of infant) must also be reported.

### **17.3. EVALUATING ADVERSE EVENTS**

An investigator who is a qualified physician will evaluate all adverse events according to the NCI Common Terminology for Adverse Events (CTCAE), version 4.0. Any adverse event which changes CTCAE grade over the course of a given episode will have each change of grade recorded on the adverse event case report forms/worksheets.

All adverse events regardless of CTCAE grade must also be evaluated for seriousness. See Table 13 below for additional guidance.

**Table 13. Evaluating Adverse Events**

An investigator who is a qualified physician, will evaluate all adverse events.

V4.0 CTCAE Grading	Grade 1	Mild; asymptomatic or mild symptoms; clinical or diagnostic observations only; intervention not indicated.
	Grade 2	Moderate; minimal, local or noninvasive intervention indicated; limiting age-appropriate instrumental ADL.
	Grade 3	Severe or medically significant but not immediately life-threatening; hospitalization or prolongation of hospitalization indicated; disabling; limiting self-care ADL.
	Grade 4	Life threatening consequences; urgent intervention indicated.
	Grade 5	Death related to AE
Seriousness	A serious adverse event is any adverse event occurring at any dose or during any use of Pembrolizumab that:	
	† Results in death ; or	
	† Is life threatening ; or places the subject, in the view of the investigator, at immediate risk of death from the event as it occurred (Note: This does not include an adverse event that, had it occurred in a more severe form, might have caused death.); or	
	† Results in a persistent or significant disability/incapacity (substantial disruption of one's ability to conduct normal life functions); or	
	† Results in or prolongs an existing inpatient hospitalization (hospitalization is defined as an inpatient admission, regardless of length of stay, even if the hospitalization is a precautionary measure for continued observation. (Note: Hospitalization to treat a preexisting condition that has not worsened is not a serious adverse event. A pre-existing condition is a clinical condition that is diagnosed prior to the use of pembrolizumab and is documented in the patient's medical history); or	
	† Is a congenital anomaly/birth defect (in offspring of subject taking the product regardless of time to diagnosis); or	
	Is a new cancer ; (that is not a condition of the study) (although serious per ICH definition, is reportable to AFT within 24 hours and AFT will report to Merck Global Safety within 2 working days).	
	Is an overdose (whether accidental or intentional). Any adverse event associated with an overdose is considered a serious adverse event for collection purposes. An overdose that is not associated with an adverse event is considered a non-serious event of clinical interest and must be reported within 24 hours.	
	Other important medical events that may not result in death, not be life threatening, or not require hospitalization may be considered a serious adverse event when, based upon appropriate medical judgment, the event may jeopardize the subject and may require medical or surgical intervention to prevent one of the outcomes listed previously (designated above by a †).	
Duration	Record the start and stop dates of the adverse event. If less than 1 day, indicate the appropriate length of time and units	
Action taken	Did the adverse event cause Pembrolizumab to be discontinued?	

Relationship to study drug	
Did Pembrolizumab cause the adverse event? The determination of the likelihood that Pembrolizumab caused the adverse event will be provided by an investigator who is a qualified physician. The investigator's signed/dated initials on the source document or worksheet that supports the causality noted on the AE form, ensures that a medically qualified assessment of causality was done. This initialed document must be retained for the required regulatory time frame. The criteria below are intended as reference guidelines to assist the investigator in assessing the likelihood of a relationship between the test drug and the adverse event based upon the available information.
 
The following components are to be used to assess the relationship between Pembrolizumab and the AE; the greater the correlation with the components and their respective elements (in number and/or intensity), the more likely Pembrolizumab caused the adverse event (AE):
	
	Exposure	Is there evidence that the subject was actually exposed to Pembrolizumab such as: reliable history, acceptable compliance assessment (pill count, diary, etc.), expected pharmacologic effect, or measurement of drug/metabolite in bodily specimen?
	Time Course	Did the AE follow in a reasonable temporal sequence from administration of Pembrolizumab? Is the time of onset of the AE compatible with a drug-induced effect (applies to studies with investigational medicinal product)?
	Likely Cause	Is the AE not reasonably explained by another etiology such as underlying disease, other drug(s)/vaccine(s), or other host or environmental factors

Relationship to Pembrolizumab (continued)	The following components are to be used to assess the relationship between the test drug and the AE: (continued)	
	Dechallenge	Was Pembrolizumab discontinued or dose/exposure/frequency reduced? If yes, did the AE resolve or improve? If yes, this is a positive dechallenge. If no, this is a negative dechallenge. (Note: This criterion is not applicable if: (1) the AE resulted in death or permanent disability; (2) the AE resolved/improved despite continuation of Pembrolizumab; or (3) Pembrolizumab(s) is/are only used one time.)
	Rechallenge	Was the subject re-exposed to Pembrolizumab in this study? If yes, did the AE recur or worsen? If yes, this is a positive rechallenge. If no, this is a negative rechallenge. (Note: This criterion is not applicable if: (1) the initial AE resulted in death or permanent disability, or (2) Pembrolizumab(s) is/are used only one time). NOTE: IF A RECHALLENGE IS PLANNED FOR AN ADVERSE EVENT WHICH WAS SERIOUS AND WHICH MAY HAVE BEEN CAUSED BY PEMBROLIZUMAB, OR IF REEXPOSURE TO PEMBROLIZUMAB POSES ADDITIONAL POTENTIAL SIGNIFICANT RISK TO THE SUBJECT, THEN THE RECHALLENGE MUST BE APPROVED IN ADVANCE BY THE U.S. CLINICAL MONITOR AS PER DOSE MODIFICATION GUIDELINES IN THE PROTOCOL.
	Consistency with Study Treatment Profile	Is the clinical/pathological presentation of the AE consistent with previous knowledge regarding Pembrolizumab or drug class pharmacology or toxicology?
The assessment of relationship will be reported on the case report forms /worksheets by an investigator who is a qualified physician according to his/her best clinical judgment, including consideration of the above elements.		
Record one of the following	Use the following scale of criteria as guidance (not all criteria must be present to be indicative of a Pembrolizumab relationship).	
Yes, there is a reasonable possibility of Pembrolizumab relationship.	There is evidence of exposure to Pembrolizumab. The temporal sequence of the AE onset relative to the administration of Pembrolizumab is reasonable. The AE is more likely explained by Pembrolizumab than by another cause.	
No, there is not a reasonable possibility Pembrolizumab relationship	Patient did not receive Pembrolizumab OR temporal sequence of the AE onset relative to administration of Pembrolizumab is not reasonable OR the AE is more likely explained by another cause than pembrolizumab.. (Also entered for a subject with overdose without an associated AE.)	

**18. DRUG INFORMATION**

**18.1. INVESTIGATIONAL PRODUCT**

The investigator shall take responsibility for and shall take all steps to maintain appropriate records and ensure appropriate supply, storage, handling, distribution and usage of investigational product in accordance with the protocol and any applicable laws and regulations.

Clinical Supplies will be provided by Merck as summarized in Table 14.

**Table 14. Product Descriptions**

Product Name & Potency	Dosage Form
Pembrolizumab 100 mg/ 4mL	Solution for Injection

**18.2. PACKAGING AND LABELING INFORMATION**

Clinical supplies will be affixed with a clinical label in accordance with regulatory requirements.

**18.3. CLINICAL SUPPLIES DISCLOSURE**

This study is open-label; therefore, the patient, the study site personnel, the Sponsor and/or designee are not blinded to treatment. Drug identity (name, strength) is included in the label text; random code/disclosure envelopes or lists are not provided.

**18.4. STORAGE AND HANDLING REQUIREMENTS**

Clinical supplies must be stored in a secure, limited-access location under the storage conditions specified on the label.

Receipt and dispensing of study medication must be recorded by an authorized person at the study site.

Clinical supplies may not be used for any purpose other than that stated in the protocol.

**18.5. RETURNS AND RECONCILIATION**

The investigator is responsible for keeping accurate records of the clinical supplies received from Merck or designee, the amount dispensed to and returned by the patients and the amount remaining at the conclusion of the study.

Upon completion or termination of the study, all unused and/or partially used investigational product will be destroyed at the site per institutional policy. It is the Investigator’s responsibility to arrange for disposal of all empty containers, provided that procedures for proper disposal have been established according to

applicable federal, state, local and institutional guidelines and procedures, and provided that appropriate records of disposal are kept.

## 19. STATISTICAL CONSIDERATIONS

This phase II study will determine if there is a benefit in progression free survival (PFS) for SCLC patients receiving pembrolizumab (Experimental arm, E) as compared to topotecan (Control arm, C) in the second-line setting. The primary endpoint will be PFS, defined as the time between randomization and disease progression or death of all causes, whichever comes first.

A total of 98 patients will be registered to this study. Taking into account 5% rate of ineligibility and cancellation, a total of 93 eligible patients will be randomized 2:1 allocation to arm E and arm C. Randomization will be implemented with dynamic allocation algorithm with the stratification factor for disease type (sensitive vs. refractory). All patients will be followed for a minimum of 6 months after the last enrollment of the study.

### 19.1. SAMPLE SIZE JUSTIFICATION

According to the findings from the phase III study studying topotecan vs CAV in the second-line treatment of SCLC patients and the phase III study comparing oral and intravenous topotecan, we expect a median PFS of 12 weeks for the control arm (C) and 20 weeks (a 67% increase) for the experimental therapy (E) in the pooled patient population with relapsed sensitive or refractory SCLC. Under the assumption of exponential survival time, it corresponds to a hazard ratio  $\lambda_E/\lambda_C = 0.60$ . Assuming an accrual rate of 4 randomized patients per month, it will take approximately 23 months to enroll 93 randomized patients (62 arm E and 31 arm C). With additional follow-up of 26 weeks (approximately 6 months) after the enrollment of the last patient, or approximately 86 events (59 arm E, 27 arm C), the study has approximately 82% power to reject the null hypothesis  $\lambda_E/\lambda_C = 1$  and accept the alternative hypothesis  $\lambda_E/\lambda_C < 1$  when the true  $\lambda_E/\lambda_C = 0.60$  using a stratified log rank test at a 1-sided significance level of 0.10.

Per above, eligible patients will be randomized with 2:1 allocation to two arms (E and C). The patients on arm C are allowed to receive pembrolizumab after progression. The final analysis is expected to take place 6 months after the last enrolled patient has been treated.

In the primary analysis, a stratified log rank test with equal weights over time will be used to test the PFS difference between two arms. As late treatment effect is often observed for immunotherapy, a weighted log rank test with Fleming-Harrington weights also will be used as a supplementary analysis to maximize the test efficiency for late treatment effect. More details can be found in the Analytic Method section.

Objective response rate (ORR) is a secondary endpoint. The sample size of the study is not determined by having adequate power to test ORR. With 62/31 patients on arm E/C, the study has approximately 82% power to differentiate  $ORR < 12\%$  versus  $ORR > 32\%$  at one-sided significance level of 0.10

## 19.2. ACCRUAL AND FOLLOW-UP

With allowance of 5% ineligible, cancelling and unevaluable, the study plans to register 98 patients. We estimate to enroll and randomize 4 patients per month and anticipate approximately 23 months to achieve the target accrual. A minimum of 6 months of follow-up is needed to evaluate the primary objective if the accrual rate is at the expected range.

## 19.3. ADVERSE EVENTS MONITORING

If 5 or more of the first 20 patients in any of the two arms experience grade 4/5 non-hematologic adverse events that are probably, possibly, or definitely related to study treatment, OR if the rate of treatment-related deaths within the first 60 days exceeds 4 or more in an arm among the first 20 patients at any time, accrual to the study will be suspended to allow for investigation. After consideration by the study team, a decision will be made as to whether accrual can be resumed, potentially with modifications to entry criteria and/or study conduct.

## 20. STATISTICAL ANALYSIS PLAN

The primary analysis will include all randomized patients but exclude ineligible patients or patients who cancel this study before receiving any protocol treatment.

The primary efficacy endpoint is PFS, which is defined as the time from the date of randomization to the date of earliest radiographic disease progression or death. If the subject does not experience radiographic disease progression or death, then the data will be censored at the date of the last disease assessment. PFS will be analyzed by Kaplan Meier methodology and compared between arm E and arm C, using a log-rank test stratified by disease type (sensitive vs refractory). A two-sided, stratified log-rank test P value will be provided. Median PFS time will be calculated and 95% confidence interval for median PFS will be presented. Overall survival (OS) will be analyzed in a similar manner as PFS.

Late treatment effect is often expected for immunotherapy. For this reason, a weighted log rank test with Harrington-Fleming weights that optimize the expected late treatment effect will be conducted as a supplementary analysis for both PFS and OS. In particular, the following three parameter settings will be used: (1)  $\rho = 0$  and  $\gamma = 0.5$ ; (2)  $\rho = 0$  and  $\gamma = 1$ ; and (3)  $\rho = 0$  and  $\gamma = 2$  (39).

The proportion of subjects with objective response as assessed by the investigator using RECIST version 1.1 will be evaluated for randomized subjects. The objective response rate will be estimated and compared between arm E and arm C, using a Cochran-Mantel-Haenszel (CMH) test stratified by tumor volume. A two-sided, stratified CMH test P value will be provided. In addition, a 95% confidence interval will be constructed for the estimated proportions. Similar analysis will be conducted for disease control rate (DCR), which is defined as the proportion of patients achieving complete, partial and stable disease after the protocol treatment.

All subjects who receive at least one dose of the study drug will be included in safety analysis. Treatment-related toxicity will be summarized by grade, type and system organ

class. Comparisons of the percentages of subjects experiencing an adverse event between arm E and arm C will be performed using Fisher's exact test.

The association between candidate biomarkers in tumor samples, including, but not limited to, CD3, CD4, CD8, FoxP3, PD-1, CD68, MHC class I and II, and PD-L1, with response will be evaluated using Wilcoxon rank sum test. The association of these biomarkers with PFS and OS will be evaluated using single-predictor Cox models.

The correlation between T-cell immunophenotypes in peripheral blood mononuclear cell samples and clinical response will be evaluated with Chi-square test.

The correlation between mutational burden in tumor specimens and objective response will be evaluated using Wilcoxon rank sum test separately for patients treated by pembrolizumab and topotecan.

The difference in neoantigen signature between SCLC tumors responding to PD-1 inhibition and those not responding to therapy will be evaluated.

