**1.2. STUDY SCHEMA (FIGURE 1)**

\*:With allowance of 5% ineligible, cancelling and unevaluable, the study plans to register 98 patients, and randomize 93.

Patients who progress on the topotecan arm may cross-over to receive treatment with pembrolizumab.

Treatment is to continue for up to 24 months post-randomization or until disease progression on pembrolizumab or an unacceptable adverse event.

Patients will be followed until death.

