## **5. RATIONALE FOR ENDPOINTS**

### **5.1. EFFICACY ENDPOINTS**

#### **5.1.1. Primary**

This randomized phase II study will assess progression free survival (PFS) as the primary endpoint based on RECIST 1.1. Given the cross-over design, PFS as opposed to overall survival was considered to be an acceptable scientific endpoint to identify the best treatment for SCLC patients in need of second-line therapy. According to the findings from the phase III study studying topotecan vs CAV in the second-line treatment of SCLC patients and the phase III trial comparing oral and intravenous topotecan, we expect only a median PFS of 12 weeks for the control arm. Further, it is anticipated that the SCLC patients responding to pembrolizumab will have a longer duration of response, which will be assessed by RECIST 1.1. The PFS rate at 6 and 9 months in each group will be assessed and compared.

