### **16.3. DEFINITIONS AND FOLLOW-UP REQUIREMENTS**

Definition of ineligible patients: A study participant who is registered to the study but does not meet all of the eligibility criteria is deemed to be ineligible.

Definition of clinical follow-up: The follow-up period where the study participant is no longer receiving treatment, but is still following the study calendar for tests, exams, and correlative endpoints (e.g., specimen collection, quality of life, disease assessments as required by the study).

Definition of survival only follow-up: The follow-up period where the study participant is monitored for long-term endpoints, is no longer receiving study treatment, and is not required to follow the study calendar for tests, exams, and correlative endpoints (e.g. specimen collection, quality of life, disease assessments as required by the study). In this follow-up period, there is a schedule in which case

report forms should be submitted, but the physician visits are based on the standard of care.

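### The primary PFS comparison drops some patients after open-label randomisation, and no all-randomised PFS analysis is planned to check it (separately, the expected event split by arm is wrong as written)

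*Combined protocol and SAP*

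**What the plan says.** Section 20 defines the set for the primary analysis: "The primary analysis will include all randomized patients but exclude ineligible patients or patients who cancel this study before receiving any protocol treatment". The stratified log-rank test of PFS follows from it. The same section describes three weighted log-rank tests, which "will be conducted as a supplementary analysis for both PFS and OS", and says OS is handled like PFS. Neither statement names another population. Objective response, by contrast, "using RECIST version 1.1 will be evaluated for randomized subjects". Section 5.1.1 adds a landmark comparison without naming a set: "The PFS rate at 6 and 9 months in each group will be assessed and compared". No section plans PFS in all randomised patients.

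Section 16.3 defines ineligibility: "A study participant who is registered to the study but does not meet all of the eligibility criteria is deemed to be ineligible". It does not say who decides, when, or on what data. Section 8.4 states that the sponsor, the investigator and the patient all know the treatment given.

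The 5% allowance falls before randomisation. In Section 1.2, "the study plans to register 98 patients, and randomize 93". In Section 19, "Taking into account 5% rate of ineligibility and cancellation, a total of 93 eligible patients will be randomized 2:1".

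Data on the excluded patients are required. Treated but ineligible patients stay on the full schedule of assessments (Section 16.4). Progression and survival data must be submitted for patients who never start treatment (Section 16.5).

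Section 19.1 assumes median PFS of 12 weeks (C) and 20 weeks (E), and states about 86 events, 59 in arm E and 27 in arm C, with about 82% power at one-sided 0.10.

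**The concern.** Randomisation protects the comparison only for the patients it allocated. Once patients can be removed after an unblinded assignment, the arms may differ for reasons other than treatment. A patient allocated to topotecan may decline because of the allocation, and an eligibility failure may come to light late. For example, adequate tumour tissue is an inclusion criterion (Section 7.1), yet Section 8.3 lets tissue reach the central laboratory up to 14 days after randomisation. The protocol does not say that the central result decides eligibility, but it does not rule this out. Writing the exclusion rule in advance does not remove the difficulty, because who meets it is still settled later.

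The control arm has only 31 patients, so one or two removals can matter. Without an all-randomised result, a reader cannot tell whether the primary finding depends on them.

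**Working it through.** **1. The plan's own figures.**
- Registration: 98 × 0.95 = 93.1, matching 93 randomised.
- Power = Φ(√(dE·dC/(dE+dC)) × |ln 0.60| − 1.2816), where dE and dC are the events by arm. With 59 and 27: √(59×27/86) = 4.304; 4.304 × 0.5108 − 1.2816 = 0.917; power 82.0%. The stated 82% is reproduced.

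**2. Effect of exclusions on the one-sided error.** The documents give no number of post-randomisation exclusions and no prognostic mix, so these are assumptions. Set-up: no treatment effect; 62 v 31 patients; two disease strata; median PFS of 20 weeks for better-prognosis and 8 weeks for poorer-prognosis patients, in equal expected shares and independent of stratum; uniform accrual over about 101 weeks plus 26 weeks; six-weekly scans; stratified log-rank test at one-sided 0.10. With each patient's prognosis drawn independently (100,000 trials):

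| Excluded | One-sided error | Change |
|---|---|---|
| Nobody | 0.107 | – |
| 2 better-prognosis controls | 0.132 | +0.025 |
| 2 poorer-prognosis controls | 0.089 | −0.018 |
| 2 controls at random | 0.108 | +0.001 |
| 2 C and 4 E, all better or all poorer | 0.109 to 0.110 | +0.002 to +0.003 |

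The absolute levels depend on how prognosis is drawn. If exactly half of each arm (as nearly as 31 allows) is better-prognosis, the error is about 0.090 with nobody excluded and about 0.111 with two better-prognosis controls excluded, a change of +0.021. Only the shift of about 0.02 is stable. The excess over 0.10 with nobody excluded, under independent draws, has nothing to do with Section 20.

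**3. Would never-treated patients add information?** Scans are timed from the first dose (Section 9.2). A patient without progression or death is handled thus: "then the data will be censored at the date of the last disease assessment". With no post-baseline scan and no recorded death, that means day 0, which in a log-rank test equals exclusion. But death is a PFS event and survival data are required. Section 3.1 cites median survival of 14 weeks on supportive care and roughly 16 to 26 weeks on topotecan. Assume exponential survival with hazard λ = ln 2/median, accrual A = 100 weeks and minimum follow-up F = 26 weeks:

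P(event) = 1 − [exp(−λF) − exp(−λ(A+F))]/(λA)

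- Median 14 weeks: 1 − (0.2760 − 0.0020)/4.951 = 0.945.
- Median 26 weeks: 1 − (0.5000 − 0.0348)/2.666 = 0.826.

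So about 83 to 95% of those who stay in follow-up would have a recorded death by the analysis.

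**4. Dilution in an all-randomised analysis.** Simulated power at hazard ratio 0.60 is 81.9% when all arm E patients are treated. It is 81.1%, 80.2% or 79.4% if 1, 2 or 3 of them are never treated and progress at the control rate.

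**5. Event split in Section 19.1 (separate point).** The same formula, with the plan's medians:
- Arm E, 20 weeks: 1 − (0.4061 − 0.0127)/3.466 = 0.886; × 62 = 55.0.
- Arm C, 12 weeks: 1 − (0.2227 − 0.0007)/5.776 = 0.962; × 31 = 29.8.
- Total 84.8, close to the stated 86.

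The stated split implies 59/62 = 95% of arm E and 27/31 = 87% of arm C with an event. That order cannot hold in expectation when arm C has the shorter median and both arms share accrual and follow-up. Swapping the medians gives 59.6 E and 27.5 C with 23 months' accrual, or 59.1 and 26.9 with 19 months, so the arms appear to have been reversed. Power with 55 and 29.8: √(55×29.8/84.8) = 4.396; 4.396 × 0.5108 − 1.2816 = 0.964; 83.3%.

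**The case against.** The strongest reply is that the plan leaves little room for such exclusions. Section 8.3 has sites verify every eligibility criterion before they enter the randomisation system. Section 10.1 starts treatment within 48 hours (72 after a Friday randomisation). Section 19 speaks of eligible patients being randomised, and no later loss is forecast. All of this stands, and it is why the effect is judged small. It does not supply the missing analysis, and Section 20 itself provides for exclusions from the randomised set.

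Several stronger readings are tempting, and the documents do not support them:
- *The rule favours pembrolizumab.* Bias needs exclusions that differ by arm and relate to prognosis. It can go either way, and the documents give no direction.
- *About 5% of randomised patients will be dropped.* The allowance sits between registration and randomisation.
- *The added analysis is pointless for never-treated patients unless they have extra scans.* Most would contribute a recorded progression or death. New imaging would also change study procedures, which Section 21.5 makes a formal amendment.
- *OS and the weighted tests have no defined population.* They are most naturally read as inheriting the primary set.
- *The event split means the trial is mis-sized.* Power is essentially unchanged.

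**Conclusion.** The gap is real: the primary PFS set can be settled after the arm is known, and nothing planned shows the result in everyone randomised. Its likely effect is small and of unknown direction. The shift of about 0.02 in one-sided error rests on assumed figures: two controls excluded, both of better prognosis, none from arm E, and a half-and-half prognostic mix with medians of 20 and 8 weeks. Random or balanced exclusions leave the error almost unchanged. The case for the change is that it is cheap, uses data already required, and lets readers check the primary result.

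The event split in Section 19.1 is a separate error, wrong as written under the plan's own medians, and adds no weight to the first point.

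**What to change.** - **Section 20:** add that PFS will also be analysed in all randomised patients by assigned arm, as a pre-specified sensitivity analysis. Alternatively, make this the primary analysis, with the eligible-and-treated set as its companion.
- **Sections 16.3 and 20:** state that ineligibility is judged only from data that existed before randomisation.
- **Reporting:** give the number excluded by arm, with reasons.
- **Section 19.1:** restate the expected events as about 55 in arm E and 30 in arm C, about 85 in total. The sample size stays as it is.

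The cost is SAP wording and one repeated analysis. No extra imaging is needed. There are two downsides. The estimate is slightly diluted, by roughly 1 to 2.5 percentage points of power if one to three arm E patients are never treated. And never-treated patients contribute mainly through recorded progression or death, possibly later than their true progression, while those who withdraw consent are still censored early.
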